11.1. Data Collection

To ensure data quality and completeness, all required data will be recorded on case report forms (CRFs) provided by the sponsor. Data will be entered onto electronic case report forms by the investigational site or designee. Case Report Forms should be completed accurately during and in a timely manner after any visit in the study. The Principal Investigator or appointed designee must review the case report forms and sign them, certifying their accuracy. Completed case report forms should be submitted to the sponsor within two weeks of completion of a study visit.

Each patient will be followed for a period of 12 months after implant according to the schedule and standard practice at the enrolling centers. There will be no additional procedures, for subjects who participate in the study. Subjects are expected to be followed at implant, then at First Follow-up ($30 \sim 100$ days), and 12-Month Follow-up (365 ± 30 days) post-implant. An intermediate visit may be scheduled in a number of patients, per physician discretion.

For subjects who are not scheduled to visit the clinic for a follow-up, a subject contact (e.g. phone call) will ensure capture of the endpoint related information, however it is strongly recommended to perform an in-office visit for at least the First Follow-up visit.

Table 3 provides an overview of the data to be collected at each visit.

				Follow Up	
Data Collected	Enrollment	Implant	First (30 ~ 100 days) Office	12-Month (365 ± 30 days) Office/Phone	Additional Office/Phone
Informed Consent	Х				
Inclusion/Exclusion	Х				
Demographic data	Х				
Medical History	Х				
LAA imaging (TEE/CT/MRI)	X ^{a,b}	Xa	Х	Xa	X ^a
Medication Regimen	Х	Х	Х	Х	Х
Current status and Vital Signs	Х	Х	Х	Х	Х
Adverse Event and Device Deficiency Reporting	X	X	X	X	Х

Table 3: Data Collection Overview

^a collected only if performed

^b within 3 calendar days prior to implant

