12.2. Statistical Analysis and Data Sets

There is no hypotheses testing in this small sample size observational study.

The Primary Effectiveness Endpoint is the occurrence of non-effective LAA closure defined as any peri-device flow > 5mm demonstrated by TEE/CT/MRI at First Follow-up.

The Primary Safety Endpoint is the occurrence of one of the following events between the time of implant and within 7 days following the procedure or by hospital discharge, whichever is later: all-cause death, ischemic stroke, systemic embolism, or device- or procedure-related events requiring open cardiac surgery or major endovascular intervention such as pseudoaneurysm repair, AV fistula repair, or other major endovascular repair. Percutaneous catheter drainage of pericardial effusions, snaring of an embolized device, thrombin injection to treat femoral pseudoaneurysm and nonsurgical treatments of access site complications are excluded from this endpoint.

Roll-in subjects are excluded from all Primary Endpoint analyses, and will be treated separately analysis set for the Primary Effectiveness analysis includes implanted subjects with a completed First Follow-up visit. The analysis set for the Primary Safety analyses will be the "intent-to-treat" analysis set, including implanted or attempted subjects. It is estimated that both Primary Effectiveness analysis and Primary Safety analysis dataset will include at least 40 subjects.

For the Primary Effectiveness Endpoint, it might be considered reasonable if up to 3 primary effectiveness endpoint events should occur in this small sample size study.

For the Primary Safety Endpoint, it might be considered reasonable if up to 3 primary safety endpoint events should occur in this small sample size study.

Missing data will not be dealt with systematically in this small sample size study. A tippingpoint analysis might be conducted for the Primary Effectiveness Endpoint to assess the impact of different assumptions about the missing data on interpretation of the results.

For Secondary Endpoint and additional analysis, different data sets could be used exploratively.

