4 GENERAL STATISTICAL METHODS

4.1 Analysis Sets

Roll-in subjects are excluded from all primary and secondary endpoints analyses and will be treated separately.

The primary analysis set for the primary effectiveness analysis will be the "per-protocol" analysis set, including implanted subjects with a completed first follow-up visit. The primary analysis set for the primary safety analysis will be the "intent-to-treat" analysis set, including implanted or attempted subjects. It is estimated that both primary effectiveness analysis and primary safety analysis dataset will include at least 40 subjects. For secondary endpoint and additional analysis, different datasets could be used exploratively.

The definitions on the different subject status and classification are provided as below:

Consent Ineligible: A subject who has signed informed consent but is found to not meet eligibility criteria will be classified as "**Consent Ineligible**". There are no FU or adverse event reporting requirements for consent ineligible subjects. Subjects determined to be Consent Ineligible do not count towards the enrollment ceiling and will not be used for analysis of the endpoints.

Intent: A subject who signs informed consent, meets eligibility criteria, but then does not undergo an implant of a WATCHMAN FLX device will be classified as "**Intent**". There are no FU or adverse event reporting or primary endpoint analysis requirements for Intent subjects. Intent subjects do not count towards the enrollment ceiling and will not be used for analysis of the endpoints.

Attempt: A subject who signs informed consent, meets eligibility criteria and has had the WATCHMAN FLX Access Sheath inserted to implant the device, but eventually does not receive a WATCHMAN FLX device will be classified as "**Attempt**". There are no FU requirements for Attempt subjects; however, adverse events will be collected up to the point of subject withdrawal. Attempt subjects count towards the enrollment ceiling and will be used for analyses of the endpoints.

Implant: A subject who is successfully implanted with the WATCHMAN FLX device will be classified as "**Implant**". These subjects are followed in accordance with the FU schedule and included in all study analyses.

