7.5 Missing data

Missing data will not be dealt with systematically in this small sample size study. For the primary safety endpoint, all attempted subjects will be eligible for evaluation, regardless of implant success. Statistical models that account for censored data will be employed for time-to-event outcomes.

When calculating rates of adverse events, missing and partial dates will be handled as shown below:

| Partial Date Description | Action Taken |
|--|--|
| Entire onset date is missing | The procedure date will be used for the |
| | onset date. |
| The month and the day of the month are | January 1 st will be used for the month and |
| missing but the year is available | day of the onset date. However, if the |
| | imputed date falls before the procedure |
| | date, then the procedure date will be used |
| | for the onset date. |
| Day is missing, but the month and year are | The 1 st will be used as the day of the onset |
| available | date. However, if the imputed date falls |
| | before the procedure date, then the |
| | procedure date will be used for the onset |
| | date. |

Missing data for primary end point analysis will follow imputation techniques

Missing data due to dropped out or withdrawn subjects will be considered as missing at random and multiple imputation will be done based on the same assumption, while missing of the follow up data will be considered as missing not at random and imputation will follow the same techniques.

A tipping-point analysis might be conducted for the Primary Effectiveness Endpoint to assess the impact of different assumptions about the missing data on interpretation of the results.

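### SAP 7.5 both disclaims and prescribes imputation for the primary endpoints, and its rule for data declared missing not at random has no adjustment for that mechanism; the tipping-point analysis is optional

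*SAP*

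**What the plan says.** SAP 7.5 opens with "Missing data will not be dealt with systematically in this small sample size study". Protocol 12.2 has the same sentence and mentions no imputation. Later in SAP 7.5 comes "Missing data for primary end point analysis will follow imputation techniques". This is not limited to effectiveness: SAP 3.1 defines both the effectiveness and the safety endpoint under the primary endpoint heading. Subjects who drop out or withdraw are taken as missing at random (MAR) and multiply imputed on that assumption. For the rest, "missing of the follow up data will be considered as missing not at random and imputation will follow the same techniques". No imputation model, number of imputations, pooling rule or adjustment is given. The section ends with "A tipping-point analysis might be conducted for the Primary Effectiveness Endpoint", and protocol 12.2 is equally non-committal.

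Other sections bear on this:

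- SAP 4.1 defines the primary effectiveness set as per-protocol, "including implanted subjects with a completed first follow-up visit", without roll-ins, and expects at least 40 subjects.
- Protocol 12.2 gives the benchmark: "it might be considered reasonable if up to 3 primary effectiveness endpoint events should occur in this small sample size study".
- Protocol 11.1 allows a telephone contact for subjects not scheduled to attend, "however it is strongly recommended to perform an in-office visit for at least the First Follow-up visit". Table 3 nevertheless heads the first follow-up as an office visit. It lists imaging there without the footnote "collected only if performed" that imaging carries at the other visits.
- SAP 7.3 item 3 has its own 30-100 day denominator, which admits event-free subjects whose last follow-up is at least 30 days after the procedure.

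**The concern.** Two statisticians could follow SAP 7.5 and produce different primary analyses, one with observed data only and one with imputed data, and both could claim compliance.

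The rule for data missing not at random (MNAR) is also wrong as written, which is more than a lack of detail. Imputation built on MAR does not become valid under MNAR because the data carry that label. Some stated departure from the observed leak risk is needed, and none is given.

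The imputation rule also sits badly with SAP 4.1. A subject who leaves before the first follow-up is outside the primary effectiveness set, so imputing that subject fits only if a supportive set is meant, and none is named.

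The leak rate is the primary effectiveness result, it is read against a count of 3, and SAP section 2 says the data may support registration elsewhere. With about 40 subjects, a few missing images can change how that count reads.

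**Working it through.** **The plan's own figures.** The only quantitative basis is the table of exact 95% intervals at n = 50. The Clopper-Pearson limits for x events in n are the 2.5% quantile of Beta(x, n-x+1) and the 97.5% quantile of Beta(x+1, n-x). All six rows reproduce; for example, 3/50 = 6% (1.3-16.5%).

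**Inputs.** From the documents: a set of at least 40, a benchmark of 3, up to 50 enrolled, and up to 5 sites with up to 2 roll-ins each (at most 10, leaving 40 to 50 non-roll-ins). Assumed, because the documents give no missing-data rate: 2 or 4 subjects without usable imaging, 3 observed leaks, and leak odds 2 to 10 times higher in missing subjects.

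**Formula.** With x leaks among n evaluable and m missing, draw p from Beta(x+0.5, n-x+0.5) and set q = OR·p/(1-p+OR·p). The mean imputed rate is (x + m·E[q])/(n+m). OR = 1 is MAR, where E[q] = (x+0.5)/(n+1).

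**(a) Missing images inside a set of 40** (first follow-up completed, no usable image):

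| | 2 missing | 4 missing |
|---|---|---|
| Observed | 3/38 = 7.9% (1.7-21.4%) | 3/36 = 8.3% (1.8-22.5%) |
| MAR | (3 + 2×3.5/39)/40 = 7.95% | (3 + 4×3.5/37)/40 = 8.45% |
| Odds ×2 | (3 + 2×0.162)/40 = 8.3% | (3 + 4×0.170)/40 = 9.2% |
| Odds ×10 | (3 + 2×0.467)/40 = 9.8% | (3 + 4×0.481)/40 = 12.3% |
| All missing leak | 5/40 = 12.5% (4.2-26.8%) | 7/40 = 17.5% (7.3-32.8%) |

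**(b) 40 evaluable, plus 2 or 4 implanted non-roll-ins outside the set** (early dropouts). At 50 enrolled this needs at most 8 or 6 roll-ins.

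| | 2 missing | 4 missing |
|---|---|---|
| Observed | 3/40 = 7.5% (1.6-20.4%) | 3/40 = 7.5% (1.6-20.4%) |
| MAR | (3 + 2×3.5/41)/42 = 7.55% | (3 + 4×3.5/41)/44 = 7.59% |
| Odds ×2 to ×10 | 7.9% to 9.3% | 8.2% to 10.9% |
| All missing leak | 5/42 = 11.9% (4.0-25.6%) | 7/44 = 15.9% (6.6-30.1%) |

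**Distance to the benchmark.** Exceeding 3 takes 4 minus the observed count among the missing: 1 leak if 3 are observed, 2 if 2, 3 if 1, and 4 if none. With 2 missing and 0 or 1 observed, 3 cannot be exceeded. With 3 observed, a single leak gives 4/40 = 10.0% (2.8-23.7%), 4/42 = 9.5% (2.7-22.6%) or 4/44 = 9.1% (2.5-21.7%).

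**The case against.** The strongest reply is that little depends on this. Nothing is tested, the benchmark triggers no action, and observed and MAR-imputed rates differ by about 0.1 percentage point. SAP 5.5 already commits to reporting patient disposition and protocol deviations, and a reader given the number of missing images can work out the worst case. All of that stands, and it limits the severity.

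Missing images may also be few. Table 3 expects an office visit with imaging at first follow-up, and protocol 11.4 calls follow-up imaging a clinical standard. A telephone contact might not count as a completed visit at all.

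SAP 7.5 could be read as a general rule with a specific exception for primary endpoints. It does not say so, and protocol 12.2 places its no-handling sentence directly after the primary-endpoint benchmarks. That reading would in any case leave the MNAR rule without an adjustment.

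A reader might infer three stronger claims that the documents do not support:

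- **That imputing dropouts is certainly empty.** SAP 4.1 calls its set the primary one, so a supportive set remains possible, though none is stated.
- **That only a tipping-point table can address the declared mechanism.** An explicit range of odds ratios would also do so.
- **That missing data will overturn the result.** No missing-data rate is given, and at low observed counts with 2 missing the benchmark cannot be exceeded.

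**Conclusion.** The point holds as a conflict in the stated rules and as an imputation rule that cannot address the mechanism it declares. It should be fixed, but it threatens no test or formal decision. The conflict covers both primary endpoints; the figures here concern effectiveness only.

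The choice between observed and MAR-imputed rates barely matters. The exposure comes from departures from MAR and is greatest when the observed count is near 3. In a set of 40 with 3 observed leaks, the observed rate of 7.9% (2 missing) or 8.3% (4 missing) could be as high as 12.5% or 17.5%. For early dropouts outside a set of 40, 7.5% could become 11.9% or 15.9%. These are worst-case bounds under assumed missing counts, not forecasts.

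**What to change.** In SAP 7.5, delete the imputation sentences for both primary endpoints and replace them with stated rules.

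- **Effectiveness.** Report observed n/N with an exact 95% interval in implanted non-roll-ins with evaluable first follow-up imaging, and use the same wording in SAP 4.1. State that the denominator in SAP 7.3 item 3 does not apply to leak, so that an unimaged subject is not counted as leak-free.
- **Safety.** Report observed events over all implanted or attempted non-roll-ins, with the number not followed to day 7 or discharge, whichever is later.
- **Tipping point.** Make it a commitment. In all implanted non-roll-ins, count from none to all of the missing subjects as leaks, give the exact interval at each step, and mark where the count exceeds 3. List the number missing and the reason for each. Show deaths before imaging on a separate line, and give the table with and without them.

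If imputation is kept instead, state the MNAR adjustment (for example a range of odds ratios), the pooling rule, and an analysis set that contains the imputed subjects.

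The cost is a SAP revision and one small table. No new data are needed. Protocol 12.2 contains no imputation rule, so its wording can be aligned at the next amendment. The downside is a reported range that may look less favourable than a single rate.
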